9.8. Data Sources

An overview of the data collection process and forms can be found in Section [9.6](#).

Registration Information

Collected from participant at enrollment

- Country of residence
- Date of first contact with registry
- Date of consent (enrollment)
- Recruitment source(s)
- Minimum data for assignment to a study cohort, including:
 - Pregnancy status
 - Diagnosis information
 - Exposure information
 - Prior enrollment status

Collected from HCP(s) – obstetric and prescriber, if needed, – at enrollment

- Minimum data for assignment to a study cohort, including:
 - Pregnancy status
 - Diagnosis information
 - Exposure information

Maternal Demographic Characteristics¹

Collected from participant at enrollment

- Date of birth
- Country of residence
- Ethnicity
- Race
- Education
- Employment status
- Household income

¹ Data collected at each study site will abide by regulatory guidelines, local privacy laws, and national provisions (e.g., date of birth and race/ethnicity will not be collected from participants in Germany). The collection of race and ethnicity data in the US will comply to the FDA guidance for industry, Collection of Race and Ethnicity Data in Clinical Trials and Clinical Studies for FDA-Regulated Medical Products.

Maternal Pre-Pregnancy Anthropometrics

Collected from participant at enrollment

- Pre-pregnancy anthropometrics (weight and height) just prior to pregnancy, weight at approximately 12 months prior to pregnancy, and weight prior to starting prescription weight-loss medication if applicable (e.g., tirzepatide or other products for the treatment of overweight/obesity)

Collected from HCP at enrollment

- Pre-pregnancy anthropometrics (weight and height) just prior to pregnancy, weight at approximately 12 months prior to pregnancy, and weight prior to starting prescription weight-loss medication (e.g., tirzepatide)

Maternal Obstetrical History

Collected from obstetric HCP at enrollment; if not available from HCP, can be collected from participant

- Number of previous pregnancies, including multiple gestations
- Outcomes of previous pregnancies (SAB, stillbirth, induced abortion, live birth)
- Complications of previous pregnancies (e.g., pregnancy-induced hypertension, pre-eclampsia, eclampsia, gestational diabetes, preterm labor, placenta previa, placental abruption, incompetent cervix, ectopic pregnancy, molar pregnancy)
- Characteristics of previous live births (preterm, SGA, LGA)
- Number of previous fetuses/infants with congenital malformations (major and minor) and contributing factors
- Family history of congenital malformations

Collected from obstetric HCP at enrollment; if not available from HCP, can be collected from participant

- Maternal and paternal family history of congenital malformations (major and minor), including specific malformation and relation of family member to mother or father

Disease Information

Collected from HCP(s) – obstetric and prescriber, if needed – at enrollment

- Maternal history of diagnosis of overweight or obesity, including date of diagnosis
- Maternal pre-pregnancy anthropometrics (weight and height) just prior to pregnancy, weight 12 months prior to pregnancy, and additionally for tirzepatide-exposed participants, weight at the time of first tirzepatide prescription
- Weight-related comorbid conditions

Baseline Pregnancy Information

Collected from obstetric HCP at enrollment only

- First day of LMP

- Method of conception
- History of fertility treatment
- Relevant maternal and paternal risk factors (medical history and exposures) for adverse pregnancy outcomes (e.g., genetic disorders, consanguinity, occupation, past chemotherapy or exposure to teratogens)

Ongoing Pregnancy Information

Collected from obstetric HCP at enrollment, end of 2nd trimester, and pregnancy outcome; at the end of the 2nd trimester and pregnancy outcome, HCPs are asked only for updates to the data previously reported

- Number of fetuses
- EDD and method of determination (i.e., LMP, ultrasound, or ART data); if ultrasound-determined, timing of ultrasound (before 14^{0/7}, before 22^{0/7}, or at or after 22^{0/7} gestational weeks)
- Prenatal tests (e.g., ultrasound, amniocentesis, maternal serum alpha-fetoprotein, chorionic villus sampling) performed, including type of test (diagnostic or screening), date of test, and results/findings (e.g., congenital malformations)
- Relevant maternal medical conditions, including, but not limited to
 - Inheritable diseases
 - Thyroid abnormalities
 - Infectious diseases (e.g., COVID-19, toxoplasmosis, cytomegalovirus, rubella, parvovirus)
 - Asthma
 - Diabetes
 - Hypertension
 - Cardiac conditions (e.g., heart failure)
 - Seizure disorder
 - Autoimmune diseases
 - Anemia
 - Depression and other psychiatric disorders
 - Hepatitis
 - Sexually transmitted diseases
 - Uterine or cervical abnormalities, including congenital uterine abnormalities
- Concurrent pregnancy-related maternal medical conditions or pregnancy complications, including
 - Preterm labor
 - Placenta previa
 - Placental abruption
 - Incompetent cervix
 - Ectopic pregnancy
 - Molar pregnancy

Maternal Exposures during Pregnancy

Collected from HCP(s) – obstetric and prescriber, if needed – at enrollment, end of 2nd trimester, and pregnancy outcome; at the end of the 2nd trimester and pregnancy outcome, HCPs are asked only for updates to the data previously reported

- Exposure to tirzepatide, including indication/reason for use (approved according to label in country of residence), dose, route, frequency, and dates/duration of exposure, if available
- Exposure to other drugs or biological products (including prescription and non-prescription drugs, dietary/herbal supplements (including folic acid and prenatal vitamins), vaccines (including COVID-19), known teratogens (see Section 9.11.1.1.4), and investigational medications), including indication/reason for use, dose, route, frequency, and dates/duration of exposure, if available
- Exposure to tobacco, alcohol, marijuana, or recreational or illicit drugs, including timing of exposure, if available

Pregnancy Outcome Information

Collected from HCP(s) – obstetric and pediatric, if needed – at or after pregnancy outcome

- Pregnancy outcome (for each fetus, classified in one of the following mutually exclusive categories: SAB, stillbirth, induced abortion, and live birth)
- Maternal outcomes: pregnancy induced hypertension, pre-eclampsia, eclampsia, gestational diabetes, maternal cardiac disease, HG, and inadequate GWG.
- Date of pregnancy outcome
- Gestational age at pregnancy outcome
- Fetal/infant sex
- Fetal/infant weight, length, and head circumference at pregnancy outcome (when available)
- Labor type (spontaneous or induced)
- Route of delivery (i.e., vaginal delivery, assisted vaginal delivery, planned caesarean delivery, or emergency caesarean delivery)
- Delivery complications
- 5 Apgar scores
- Congenital malformations (major and minor), including post-mortem findings for fetal losses and assessment of potential contributing factors
- Maternal weight at (just prior to) pregnancy outcome
- For live births, prolonged hospitalization after delivery and reason
- For a non-induced fetal loss (SAB, stillbirth), factors that may have had an impact on the fetal loss and attribution
- For induced abortion, reason (e.g., finding on prenatal test, risk to mother's health, undesired pregnancy)

Infant Outcome Information

Collected from pediatric HCP at 4 and 12 months post-delivery

- Infant weight, length, and head circumference at birth (if not provided at pregnancy outcome) and at 4 and 12 months of age
- Achievement of the developmental milestones in each Centers for Disease Control and Prevention (CDC)-defined category (social/emotional, language/communication, cognitive, and movement/physical development) at 4 and 12 months of age
- Congenital malformations (major and minor) and assessment of potential contributing factors
- Infant death, including date and cause of death
- Infant illnesses (e.g., neonatal hypoglycemia), infections, and hospitalizations
- Breastfeeding information, including breastfeeding start/stop dates, maternal medicinal and recreational exposures during breastfeeding, and low milk supply

Targeted Follow-up Information

Collected from HCP(s) – obstetric and/or pediatric – at any time after pregnancy outcome

- Details of congenital malformations (major or minor) or other conditions
- Etiology
- Exposures that may have had an impact on the outcome
- Additional factors that may have had an impact on the outcome
- Specific questions requested by the sponsor and/or the birth defect evaluator

Data collection may be restricted in some cases due to country-specific privacy/data protection regulations.

Data Reconciliation

Although data may be collected from multiple reporters, a hierarchy will be applied during analysis that prioritizes the response from the reporter that is most likely to have the most accurate information on a per variable basis. For example, for disease characteristics and medicinal exposures, the primary position would go to information reported by the prescribing HCP, followed by the obstetric HCP, pediatric HCP, and the patient. Pregnancy information would have the obstetric HCP as the primary reporter, followed by the prescribing HCP, pediatric HCP, etc. Infant-related variables will have pediatric HCP as primary, followed by obstetric HCP, and prescribing HCP. Generally, HCP-reported information will always be used for all reporting, with two exceptions: patient-reported exposures may be used for initial cohort classification while HCP verification is pending and patient-reported LMP may be used for pregnancy dating if both the HCP-reported LMP and EDD are missing.

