The exploratory objective is to describe and compare the prevalence of additional maternal, fetal and infant outcomes of interest between pregnant individuals treated with tirzepatide for weight management during pregnancy and the two comparator cohorts of pregnant individuals (AOM active comparator cohort and AOM unexposed comparator cohort). The exploratory outcomes of interest are as follows:

- Hyperemesis gravidarum
- Inadequate gestational weight gain
- Maternal cardiac disease (e.g., heart failure, cardiomyopathies)
- Large-for-gestational age; and
- Infant rapid weight gain

Study design

This is a prospective, observational cohort study designed to evaluate the association between tirzepatide treatment for weight management during pregnancy and subsequent maternal, fetal, and infant outcomes.

Population

The study population will include three cohorts of pregnant individuals:

- Tirzepatide exposed cohort: A cohort of individuals who are treated with tirzepatide for weight management during pregnancy
- Anti-obesity medication (AOM) active comparator cohort: A cohort of individuals who are treated with pharmacotherapy other than tirzepatide or other therapies with GLP-1 RA activity for weight management during pregnancy. The comparator AOMs may include, but not limited to, orlistat, setmelanotide, and naltrexone-bupropion.
- AOM unexposed comparator cohort: A cohort of individuals who have obesity or are overweight with at least one weight-related comorbid condition at the time of conception; and who are not treated with tirzepatide, GLP-1 RA therapies, or any products for weight management during pregnancy.

Variables

Individuals will be considered treated during pregnancy if at least one dose of a product is taken during pregnancy or during the period equal to up to 5 times the product's half-life prior to conception. Based on the half-life of tirzepatide (5 days), individuals will be considered as treated with tirzepatide during pregnancy if a dose is taken within 25 days prior to conception. The primary outcome of MCMs will be adjudicated by independent experts, blinded to exposure, using the CDC's MACDP system or EUROCAT. Secondary and exploratory outcomes will be ascertained by assessment of HCPs who provide care during pregnancy and/or pediatric care.

Covariates of interest will include demographics, risk factors for the study outcomes, comorbidities, concomitant medications, and predictors of treatment with tirzepatide.

Data sources

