9.7.3. Outcome Definitions and Ascertainment

Table 9.3 presents the definitions of the outcomes. For outcomes not simply reported by the HCP, additional information on outcome ascertainment is provided.

Table 9.3. Definitions of Outcomes

Outcome	Clinical Definition	Operational definition
Major congenital malformation (MCM)	An abnormality of body structure or function that is present at birth; is of prenatal origin (i.e., birth defect); has significant medical, social, or cosmetic consequences for the affected individual; and typically requires medical intervention ⁴⁸	
The registry defines and codes MCMs with criteria specified by the CDC MACDP (Annex 3).⁴⁹ When participants who reside in Europe are enrolled, MCMs will also be defined and coded using the criteria specified by the EUROCAT⁵⁰ (Annex 3).
 
Exclusion criteria for MCM analyses include exposure to known teratogens and/or investigational medications, and/or congenital infectious agents (e.g. zika, TORCH, HIV). To avoid misattribution of the malformation to the medication, MCMs not known to be associated with medication exposure, such as chromosomal abnormalities, genetic syndromes, fetal alcohol syndrome, prematurity-related conditions in infants born at <36 gestational weeks (e.g., patent ductus arteriosus, patent foramen ovale, inguinal hernias, or undescended testes), and positional effects (e.g., hip dislocation due to breech position or abnormal skull shape due to crowding by multiple fetuses), will not be considered MCMs in the statistical analyses.⁵¹
 
Adjudication process: A panel of 2–3 independent experts in clinical genetics and neonatology, blinded to exposure, will review all malformations reported to the registry among live and non-live births and classify them using the CDC's MACDP system for US-reported cases (and EUROCAT, for EU-reported cases). Additionally, the birth defect evaluators will provide the organ system involved, etiology of the defect (e.g., chromosomal abnormality, prematurity), and approximate timing of the development of observed defects. If additional information is needed to aid in classification, the birth defect evaluators will request additional information using the targeted follow-up process outlined in Section 9.6.2. These assessments will be recorded in the study database. If there is a discrepancy, a third expert will independently review and code the case serving as tie breaker. These reviews will occur soon after the malformation is reported. Additional reviews will occur if new information is received for the case. The SAC that will not be blinded to exposure will assess the possible temporal association between exposure (to tirzepatide) and the development of observed defects. Additionally, the SAC will review all malformation cases reported to the registry and reach consensus on the coding of each case. The sponsor will not be involved in any activities related to case review or adjudication.

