Hyperemesis gravidarum	Uncontrolled vomiting requiring hospitalization, severe dehydration, muscle wasting, electrolyte imbalance, ketonuria, and weight loss of more than 5% of body weight ⁵⁷	As reported by HCP.
Inadequate gestational weight gain	Gestation weight gain that is below the recommended range at term based on pregnancy weight category	The registry will use the 2009 gestational weight gain guidelines of the Institute of Medicine ⁵⁸ to determine inadequate maternal weight gain at term per maternal pre-pregnancy BMI category in singleton and twin gestations.
Spontaneous abortion (SAB)	An involuntary fetal loss or the expulsion of the products of conception occurring at <20 gestational weeks	Section 9.7.5 provides information on the methods used to calculate gestational age.
Stillbirth	As defined by the ACOG, an involuntary fetal loss occurring at ≥ 20 gestational weeks or, if gestational age is unknown, a fetus weighing ≥ 350 g ⁵⁹	Section 9.7.5 provides information on the methods used to calculate gestational age.
Induced abortion	An intervention that is intended to terminate a suspected or known ongoing intrauterine pregnancy and that does not result in a live birth ⁶⁰	As reported by HCP.
Preterm birth	A live birth occurring at <37 gestational weeks	Section 9.7.5 provides information on the methods used to calculate gestational age.

Outcome	Clinical Definition	Operational definition
Small for gestational age (SGA)	Birth weight <10th percentile for sex and gestational age using standard growth charts for full and preterm live-born infants ⁶¹	For the determination of SGA, the registry will utilize the sex-specific international growth reference standards from the INTERGROWTH-21st for those born between 24 ^{0/7} and 42 ^{6/7} gestational weeks. ^{62,63} The INTERGROWTH-21st standards are the latest available global reference standards, representing contemporary information from an international, multi-ethnic, diverse population, and have been specifically developed for modern research.

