- For SAB and preterm birth, prevalence will be calculated among the subset of individuals who are enrolled in the registry prior to 20 and 37 gestational weeks, respectively. Additionally, for these time-to-event outcomes, data will be censored at appropriate time points: 20 gestational weeks for SAB and 37 gestational weeks for preterm birth.
- For pregnancy complications prevalence will be calculated according to the following assessment windows:
 - Pregnancy induced hypertension reported for the first time among participants after 20 weeks gestation.
 - Pre-eclampsia/eclampsia reported among participants after 20 weeks of gestation.
 - New-onset gestational diabetes reported among participants at any time during pregnancy
 - Inadequate maternal weight gain reported among participants at any time during pregnancy.
 - HG reported among participants anytime during pregnancy.
- Prevalence will be calculated at multiple time points for postnatal growth deficiency, rapid infant weight gain, and infant developmental delay will be assessed at 4 months (± 2 weeks) and 12 months (± 2 weeks) of infant age. At each time point, prevalence will be calculated among infants with data available for the particular outcome at that time point. If there is no assessment available at 4 and/or 12 months, available data will be evaluated based on the actual time of assessment (e.g., if the infant was measured at 6 months, these data will be compared to the values appropriate for a 6-month-old infant based on the growth charts). However, only development at 4 and 12 months will be reported as study outcomes, results from other time points will be reported in a separate category.

The unweighted univariate regression will be used to compare the crude (unadjusted) RRs for all outcomes. Adjusted methods will incorporate weights estimated using the IPTW method to balance the cohorts with regard to observable covariates (Section 9.11.2.4). A weighted generalized linear model using a binomial family and a log (relative risk) link will be employed to estimate an adjusted relative risk.

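### Inadequate gestational weight gain has inconsistent case rules (registry-derived at term in Table 9.3, reported at any time in 9.11.2.2) and a Table 9.7 denominator not limited to term

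*Protocol*

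**What the plan says.** Five places in the protocol bear on this outcome.

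- **Section 9.7.3, Table 9.3.** The clinical definition is "Gestation weight gain that is below the recommended range at term based on pregnancy weight category". The operational definition has the registry use the 2009 Institute of Medicine guideline "to determine inadequate maternal weight gain at term per maternal pre-pregnancy BMI category in singleton and twin gestations". The sentence introducing the table explains the extra text: "For outcomes not simply reported by the HCP, additional information on outcome ascertainment is provided".
- **Section 9.8, Pregnancy Outcome Information.** The block is headed "Collected from HCP(s) – obstetric and pediatric, if needed – at or after pregnancy outcome" and contains "Maternal outcomes: pregnancy induced hypertension, pre-eclampsia, eclampsia, gestational diabetes, maternal cardiac disease, HG, and inadequate GWG". The same block also collects "Maternal weight at (just prior to) pregnancy outcome".
- **Section 9.11.2.2, assessment windows.** Prevalence is to be calculated from "Inadequate maternal weight gain reported among participants at any time during pregnancy".
- **Section 9.11.2.2, Table 9.7.** The numerator cell gives only the outcome's name. The denominator is everyone in the analysis population.
- **Abstract, Variables.** "Secondary and exploratory outcomes will be ascertained by assessment of HCPs who provide care during pregnancy and/or pediatric care".

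**The concern.** A case can be identified in two ways that need not agree. Under Table 9.3 a woman is a case if her measured gain at term falls below the range for her BMI category. Under the 9.11.2.2 window she is a case if someone reported inadequate gain at some point. A woman below range with no report is a case under the first rule and not under the second. A woman reported as low whose final gain is in range is the reverse.

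The reporting HCPs also supply the tirzepatide exposure data (9.8, Maternal Exposures during Pregnancy), and blinding to exposure is stated only for malformation adjudication. Section 7.2 describes a drug that lowers body weight and calorie intake, so knowledge of exposure could plausibly influence whether low gain is recorded. Weighting on the propensity score balances covariates; it does not repair misclassification of the outcome.

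The denominator is a separate mismatch. A definition that applies at term is divided by a population that includes preterm births and fetal losses.

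**Working it through.** **1. The rules side by side**

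| Place | Source | Timing | Population |
|---|---|---|---|
| Table 9.3 | Registry, guideline ranges | At term | Singleton and twin |
| 9.8 | HCP-supplied item | At or after outcome | Not stated |
| 9.11.2.2 window | Reported, reporter not named | Any time in pregnancy | Participants |
| Table 9.7 | Not stated | Not stated | Whole analysis population |
| Abstract | HCP assessment | Not stated | Not stated |

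Table 9.3 and the 9.11.2.2 window differ on source and timing. Table 9.3 and Table 9.7 differ on population. Nothing states which rule forms the numerator.

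**2. How the protocol treats similar outcomes**

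SGA, LGA, postnatal growth deficiency and rapid infant weight gain are also classified against a reference standard. For these, 9.8 collects weights and other measurements and asks for no HCP label. Inadequate weight gain is the exception.

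**3. The plan's own figures**

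Table 9.4 uses a 15% reference prevalence and needs 42 per cohort for RR 3. With the Walters approximation, two-sided alpha 0.05 and 1:1 allocation, power = Φ(|asin√(p₂ − 1/2n) − asin√(p₁ + 1/2n)|·√(2n) − 1.96). With p₁ = 0.15 and p₂ = 0.45, n = 41 gives 0.798 and n = 42 gives 0.809, so 42 is reproduced. The other eight values in the row also match. No stated figure is in dispute.

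**4. Size of the denominator mismatch**

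Inputs: 90% of enrolled pregnancies end in live birth (9.9.1) and 8.47% of singleton live births are preterm (Table 9.4). Assumption: the singleton rate is applied to all live births.

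- Share reaching term: 0.90 × (1 − 0.0847) = 0.824, so about 18% do not.
- Analysed per cohort: 364 × 0.9 = 328. Reaching term: 328 × 0.824 = 270. Not reaching term: 58.
- If only term cases enter the numerator, 15% among term pregnancies becomes 15% × 0.824 = 12.4% in Table 9.7.
- For an assumed 10% to 25% not reaching term, 15% becomes 13.5% to 11.3%.
- If those shares differ between cohorts, the ratio moves with no difference in weight gain at term: 0.75/0.90 = 0.83, or 0.90/0.75 = 1.20.

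If pregnancies ending early were instead scored against a range meant for term, some would become cases because they ended early.

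**5. Can the reporting bias be sized?**

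Take a true prevalence of 15% in both cohorts, every true case captured, and false-report rates f₁ (tirzepatide) and f₀ (comparator). Then RR = (0.15 + 0.85f₁)/(0.15 + 0.85f₀).

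| Assumed rates | RR if higher in tirzepatide | RR if higher in comparator |
|---|---|---|
| 5% and 2% | 0.1925/0.1670 = 1.15 | 0.87 |
| 10% and 3% | 0.2350/0.1755 = 1.34 | 0.75 |
| 15% and 5% | 0.2775/0.1925 = 1.44 | 0.69 |

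Equal rates give 1. The protocol contains no reporting rates, so neither the direction nor the size follows from it.

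**The case against.** The strongest defence is that the protocol says where definitions are found. Section 9.4 sends the reader to 9.7.3 for the definition and ascertainment of the exploratory outcomes, and there this outcome receives registry-derivation text while its neighbours are left to HCP report. The 9.11.2.2 bullet is a window, not a definition. The 9.8 entry may only list topics covered by the outcome form, which is not shown. The inputs for the calculation are collected. All of that is fair, and it makes Table 9.3 the natural governing text. It does not remove the 9.11.2.2 rule, which says how prevalence will be calculated and differs on both source and timing.

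A reader might infer that the protocol makes this an HCP-reported event at any time in pregnancy. No single place says both: 9.8 names the HCP but collects at or after outcome, and the 9.11.2.2 window says any time but names no reporter. The items listed for enrolment and the end of the second trimester do not include inadequate weight gain, so a mid-pregnancy flag has no listed route into the data.

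A reader might also infer a bias towards harm for tirzepatide. That requires the reported version to be used and unequal reporting in one particular direction. The documents show neither.

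**Conclusion.** The inconsistency holds. Source, timing and population are each stated in ways that cannot all be followed. If the 9.11.2.2 rule is applied, the result is not the outcome defined in Table 9.3, and it rests on reports from HCPs who know the exposure. That is a conditional risk of unknown direction and size. The denominator mismatch can be roughly sized at about 18% of the analysis population, or 58 of 328 per cohort, given the protocol's live-birth assumption and general-population preterm rate.

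The outcome is exploratory, and Section 9.11.2 makes its p-values nominal. The primary analysis, the target of 364 per cohort and the Table 9.4 figures are unaffected. This is a minor item.

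**What to change.** - **Section 9.11.2.2, windows:** replace the reported-at-any-time bullet with the Table 9.3 derivation, using pre-pregnancy weight and height and the weight just before outcome, by one algorithm in all cohorts.
- **Section 9.8:** keep the weights, and state that any HCP report of inadequate weight gain is descriptive only and does not define a case.
- **Abstract:** except this outcome from the statement on HCP assessment.
- **Table 9.7:** write out the numerator, and restrict the denominator to singleton and twin pregnancies reaching term with both weights available. Term should be stated; 37 weeks or more would match the protocol's preterm definition.

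The denominator change must accompany the numerator change. Otherwise preterm births and fetal losses are either scored against a term range or counted as non-cases.

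The cost is wording, plus the loss from this outcome of women with a missing weight, a pregnancy ending before term or a higher-order multiple. The comparison becomes conditional on reaching term, which the report should say. With 270 instead of 328 per cohort at 15% prevalence, power for RR 3 stays near 100%, so the Table 9.5 entry stands. For RR 2 it goes from 0.995 to 0.985, and for RR 1.5 from 0.66 to 0.57, before any loss to missing weights or propensity weighting.
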